2.2 BACKGROUND

Investigational drug product - Galnobax®

Galnobax® is a new gel formulation to be administered topically containing a pharmaceutically approved drug substance Esmolol hydrochloride. Esmolol hydrochloride is a beta1-selective (cardioselective) adrenergic receptor blocking agent with a short duration of action (elimination half-life is approx. 9 minutes) and no intrinsic sympathomimetic or membrane stabilizing activity at therapeutic dosages. Esmolol hydrochloride inhibits the beta1 receptors located chiefly in cardiac muscle, but this preferential effect is not absolute and at higher doses it begins to inhibit beta2 receptors located chiefly in the bronchial and vascular musculature. Esmolol hydrochloride is metabolized by esterase from erythrocytes and is not metabolized by liver or kidney.²⁰

Non-clinical Studies

The non-clinical studies on the drug substance of Galnobax® demonstrates that it is capable of pleiotropic actions to heal DFU such as:²¹

- Aldose reductase inhibition
- Inhibition of sorbitol accumulation in erythrocytes and inhibition of Advanced Glycosylated End products formation
- Faster wound closure in scratch assay under high glucose environment

The non-clinical studies on Galnobax® using globally accepted animal models for evaluating pharmacological parameters for healing of DFU such as diabetic Lewis Rats (for pharmacokinetic studies) and diabetic Hairless rats have demonstrated that;

- a. Galnobax® closes the diabetic wound faster than the control group for up to 10 days.
- b. While the wound epithelialization in the treatment groups is like the control groups, it is amply demonstrated that the Galnobax® group had improved induction of internal healing processes such as endogenous nitric oxide production in inflammatory and proliferative phase and higher collagen formation and deposition in the remodeling phase of diabetic wound healing than the control group resulting in better quality of wound healing.
- c. Better healing in Galnobax® treated wounds is also demonstrated by laser Doppler studies which show higher average flux of blood flow in vehicle treated groups.
- d. Galnobax® has multiple therapeutic actions such as Nitric oxide induction, Collagen turnover at the wound site, neo-vascularization and anti-oxidant effects contribute to faster healing and closure compared to the control.

Additionally, the non-clinical PK studies evidence that by application of Galnobax®, Esmolol hydrochloride is minimally absorbed (less than 10 ng/mL in rats and average maximum concentration of 30 ng/mL in minipigs) into systemic circulation, thereby evidencing that Galnobax® is safe to use in the treatment of DFU. The above observations and the fact that Esmolol hydrochloride is a pharmaceutically approved drug with well elucidated safety profile, suggest that Galnobax® has significantly favorable risk/benefit profile.²¹

Clinical Studies

The efficacy analysis of Phase 1/2 clinical Study of Galnobax® numerically establishes that Galnobax® 14% treatment has advantage in terms of area and volume reduction over the Vehicle and Galnobax® 20%. This advantage of Galnobax® 14% is more pronounced in hard to heal DFU:

- **In plantar DFU:** Galnobax® 14% showed 98.1% area closure Vs 75.8% for Placebo. The median time for complete wound closure was 35 days for Galnobax® 14% Vs 64 days for Placebo²¹
- **In older DFU:** On DFUs older than 8 weeks at baseline, Galnobax® 14% group showed complete closure in 75% Subjects Vs 43% in Placebo group²¹

The safety analysis of Phase 1/2 clinical Study establishes and reconfirms the findings of the non-clinical studies that Galnobax® is safe for long term use (tested for 12-weeks) in both 14% and 20% concentrations. Overall 29 adverse events (AEs) were observed in the Study and only two were related to the Study treatment. These two AEs were local mild allergic reactions which were found to be reversible. The safety of Galnobax® is further reinforced by the pharmacokinetic analysis of Phase 1/2 clinical Study which establishes that the systemic concentration of its drug substance (Esmolol hydrochloride) was below quantification limit (10 ng/mL) at any time during the

treatment period, irrespective of wounds of different sizes and doses of Galnobax®. This observation is significantly lower than:

- Systemic concentration of 868-1470 ng/mL observed for approved doses of intravenous Esmolol hydrochloride
- Human peak plasma concentration of 500, 1200 and 2500 ng/mL respectively observed for the infusion of Esmolol hydrochloride at the rate of 100, 250 and 500 µg/kg/min²²

Considering the above facts, it is proposed to investigate Galnobax® 14% in a Phase 3 Study to establish safety and efficacy with statistical significance.

2.3 RISK/BENEFIT ASSESSMENT

2.3.1 KNOWN POTENTIAL RISKS

Phase 1/2 study of Galnobax® on 44 DFU Subjects reported the following:

- a. No deaths were reported during the study.
- b. There were 4 SAEs (arthritis bacterial, infected skin ulcer, gastroenteritis, and cellulitis) reported during the study, all in the Galnobax® 20% group and none determined by the Investigator as related to the study drug. All these SAEs were resolved during the study.
- c. There were 29 AEs of which only 2 were determined by the Investigator as related to the Study drug (TEAEs) with 1 Subject each in the Galnobax® 14% [TEAE: skin discoloration] and Galnobax® 20% [TEAE: erythema] groups. Both these events were non-serious and mild in intensity which were reversible on discontinuation of drug. None of the vital signs and Electrocardiogram (ECG) abnormalities were reported as TEAEs.
- d. Furthermore, the drug substance used in Galnobax® (Esmolol hydrochloride) is approved for intravenous application with all reported AEs being mild, transient and reported to be reversible after discontinuation of dosing in spite of systemic concentration of 868-1470 ng/mL²³ and human peak plasma concentration of 500, 1200 and 2500 ng/mL respectively at the infusion rate of 100, 250 and 500 µg/kg/min²². As against this, the clinical pharmacokinetic (PK) studies of Galnobax® conducted as part of the Phase 1/2 study demonstrated that the systemic concentration of its drug substance (Esmolol hydrochloride) through topical administration was below quantification limit (10 ng/mL) at any time during the treatment period, irrespective of wounds of different sizes and doses of Galnobax®. This low systemic absorption and localized action is also substantiated by non-clinical PK studies conducted in Lewis rats and in minipigs.²¹

The non-clinical toxicity studies of Galnobax® showed slight irritation in rabbit model which was found to be reversible and did not elicit skin sensitization in guinea pig model.

All of the above is sufficient to conclude that Galnobax® with no deaths, no SAEs related to the drug, only 2 drug related AEs which were reversible and minimal systemic absorption (way below approved tolerated concentrations) as established in Phase 1/2 study has a favorable human safety profile.²¹

2.3.2 KNOWN POTENTIAL BENEFITS

Basic science and translational investigation are intensively researching the key abnormalities responsible for altering the wound-healing process in DM.²⁴ Yet, in spite of some available therapies, DFU still remains ineffectively treated in 67% of the cases resulting in lower extremity

amputations in about 15% of the cases.²⁵ Thus, DFU continues to be a strong medical unmet need and calls for a new drug which can comprehensively address the underlying structural and functional abnormalities through which DM impairs wound healing. There is a dire need to improve the clinical outcomes and improve the quality of life of Subjects with DFUs.

14% Galnobax®, a gel formulation for topical administration with an approved drug substance (Esmolol hydrochloride) with favorable data from the Phase 1/2 clinical study and non-clinical studies has not only been found safe, demonstrated more comprehensive ability to address the underlying structural and functional abnormalities through which DM impairs wound healing but has also demonstrated potential to be more effective in delivering better outcomes namely:²¹

- a. Complete closure in older non-healing DFUs compared to the Vehicle (75% v/s 43%)
- b. Faster complete closure compared to the Vehicle (35 days v/s 64 days)
- c. Higher area reduction over Vehicle in 12-weeks treatment (98.1% v/s 75.8%)
- d. No local reaction or risk of long term use of drug is anticipated

In addition, Galnobax® provides a tissue adherent thermo-reversible polymeric gel suitable for application on chronic wounds.²¹

Therefore, there are sufficient known and well evidenced benefits of Galnobax® for the treatment of DFU.

2.3.3 ASSESSMENT OF POTENTIAL RISKS AND BENEFITS

The fundamentals of good clinical care include adequate off-loading, frequent debridement, moist wound care, treatment of infection, and revascularization of ischemic limbs. Even when properly managed, the wounds may not heal in a timely fashion thereby leaving them open to getting complicated by intervening infection, hospitalization, amputation and, thus, to be costlier because of the increased utilization of healthcare resources.²⁶

Considering the clinically beneficial outcomes established in Phase 1/2 study, findings of non-clinical pharmacological and toxicological information and ample existing human safety data on its drug substance (Esmolol hydrochloride), positions Galnobax® as having a favorable Risk / Benefit profile to necessitate the proposed clinical Phase 3 study.

In this Phase 3 Study, care has been taken to ensure that in the event of any drug related adverse event, the Investigator will assess risk/benefit of Galnobax® to the Subject before deciding continuation of treatment. In addition, the treatment will be administered to the Subject by a trained Nurse, which will further minimize risk to the Subject, if any.

3 OBJECTIVES AND ENDPOINTS

OBJECTIVES	ENDPOINTS	JUSTIFICATION FOR ENDPOINTS
Primary		

 To assess the efficacy of Galnobax® in terms of proportion of Subjects achieving Target Ulcer Closure within 12-week Treatment Phase upon application of Galnobax® plus Standard of Care as against only Standard of Care treatment, as assessed by the blinded Investigator 	
The efficacy assessment will involve Galnobax® plus Standard of Care and only Standard of Care groups
 
Efficacy endpoints:
 
Proportion of subjects achieving Target Ulcer Closure within 12-week Treatment Phase, as assessed by blinded Investigator
	Complete wound closure of a chronic, nonhealing wound is one of the most important objective and clinically meaningful wound healing endpoint
Secondary		
Efficacy	Efficacy endpoints	

 To compare Time to Target Ulcer Closure within the 12-week Treatment Phase, upon application of Galnobax® plus Standard of Care as against only Standard of Care treatment, as assessed by the blinded Investigator 	
 Time to Target Ulcer Closure during the 12-week Treatment Phase, as assessed by the blinded Investigator 	This endpoint evaluates clinically meaningful reduction in the time to Target Ulcer Closure using a time-to-event analysis (the event being first observation of complete closure)

 To compare proportion of Subjects achieving Target Ulcer Closure till End of Study upon application of Galnobax® plus Standard of Care as against only Standard of Care treatment, as assessed by the blinded Investigator 	
 Proportion of Subjects achieving Target Ulcer Closure till End of Study, as assessed by the blinded Investigator 	This endpoint is for evaluating sustained effect of the treatment post its discontinuation
Safety		

 To investigate the safety of Galnobax® treatment during the Study 	
 Proportion of Subjects with treatment emergent adverse events (TEAEs) 	This endpoint evaluates safety of Galnobax® by assessing TEAEs


To investigate the safety of Galnobax® vehicle for establishing non-deleterious effects of Vehicle on wound healing	
Proportion of Subjects with events related to the local wound assessment of Target Ulcer in Vehicle plus Standard of Care group	This endpoint evaluates events related to local wound assessment of Target Ulcer in Vehicle plus Standard of Care group
---	---	---

4 STUDY DESIGN

4.1 OVERALL DESIGN

This Study is a Phase 3, multicenter, randomized, double-blind, parallel-group Study designed to evaluate the safety and efficacy of Galnobax® plus SoC versus only SoC, in treating DFU in adults with diabetes mellitus (DM). In addition, Study is designed to evaluate safety of Vehicle plus SoC versus only SoC in Subjects with DFU to investigate deleterious effects of Vehicle on wound healing, if any.

For this purpose, the Subjects will be randomized in 3:3:1 ratio into one of the following groups:

- Group 1: Galnobax® 14% gel plus SoC
- Group 2: SoC only
- Group 3: Vehicle plus SoC

Total number of Subjects in the Study: This Study will have FAS Population (Efficacy Evaluable Population) of a minimum of 240 Subjects in Group 1 and Group 2 (minimum of 120 in each Group). To ensure this and assuming 20% drop out rate, the population of two groups would be maximum of 300 Subjects. In addition, for investigating the effect of vehicle on wound healing, Vehicle plus SoC group will recruit up to 50 Subjects. Thus, overall 350 Subjects will be recruited in the Study.

No. of investigational sites: This Study will be conducted at approximately 40 sites across India with competitive recruitment amongst sites.

Maximum duration of a Subject in the Study: The maximum total duration of Subject in the Study will be 25 weeks spread over three phases in following sequence:

- Screening Phase of 1-week (7 + 3 days)
- Treatment Phase of a maximum of 12-weeks (84±3 days) starting with Baseline visit
- Follow-Up Phase of 12-weeks (84±5 days). This will comprise of Closure Confirmation period of 4 weeks (28±3 days) and Observation period of 8 weeks (56±5 days).

Subject Number Assignment: The Subjects will be assigned randomization number using an interactive web-based randomization system (IWRs). Prior to randomization, Subjects will be stratified by location (plantar or non-plantar) and size ($<5\text{ cm}^2$ or $\geq 5\text{ cm}^2$) of the Target Ulcer solely for the purpose of bringing homogeneity among the three treatment Groups in proportionately. Once a randomization number has been assigned, it cannot be re-assigned to any other Subject.

Application of Treatment: Subjects in the Study will receive treatment twice daily during the 12-weeks of Treatment Phase or up to the Target Ulcer Closure, whichever is earlier. During this period, the twice daily treatment to the Subjects in all the arms of the Study will be administered

by the Study Nurse. Unless recommended by the Investigator otherwise, SoC during the Follow-Up Phase will be self-administered by the Subject.

Visit Schedule of the Subjects: Subjects in the Study will visit investigational site once a week during the 12-week Treatment Phase for wound measurement and for completing Study related assessments and procedures. In the Follow-Up (FU) Phase, the Subjects will visit investigational site at week 14, 16, 20 and 24.

Rules for Subject progression in the Study

The Subject progression in the Study will happen as per rules given in Table 1

Table 1 Subject progression as per condition of Target Ulcer

Sr. No.	Target Ulcer Closure within Treatment Phase	Reopened in Closure Confirmation period?	Action to be taken in the Study
1	Not closed	Not applicable	Proceed to Follow-Up Phase
2	Closed	No	Continue the Follow-Up Phase
		Yes	If reopened within 12-weeks from Baseline visit, continue treatment till EOT or Target Ulcer Closure, whichever is earlier and then proceed to Follow-Up Phase. If reopened after 12-weeks from Baseline visit, continue the Follow-Up Phase

The nomenclature used of various Study visits will be as follows:

Screening Visit: V1 or Day -10 to -7 (minus ten to minus seven) or Week -1 (minus one)

Treatment Visits:

V2 or Day 0 or Week 0 (also referred to as Baseline visit)

V3 or Day 7 or Week 1

V4 or Day 14 or Week 2

V5 or Day 21 or Week 3

V6 or Day 28 or Week 4

V7 or Day 35 or Week 5

V8 or Day 42 or Week 6

V9 or Day 49 or Week 7

V10 or Day 56 or Week 8

V11 or Day 63 or Week 9

V12 or Day 70 or Week 10

V13 or Day 77 or Week 11

V14 or Day 84 or Week 12 or End of Treatment (EOT)

Follow-Up (FU) Visits:

FU1 or V15 or Day 98 or Week 14 (also referred to as Closure Verification visit)

FU2 or V16 or Day 112 or Week 16 (also referred to as Closure Confirmation visit)

FU3 or V17 or Day 140 or Week 20

FU4 or V18 or Day 168 or Week 24 or End of Study (EOS)

4.2 SCIENTIFIC RATIONALE FOR STUDY DESIGN

The Study consists of about one week (7 to 10 days) of Screening period to confirm the suitability of Subject for the Study and to restrict recruitment of Subjects having healing ulcers. The Study has Treatment Phase of up to 12-weeks (84 ± 3 days) or the Target Ulcer Closure, whichever happens earlier as the Investigational Product (IP) requires 12-weeks of treatment to establish its efficacy. In view of this, if the Target Ulcer re-opens within these 84 days, the Subject will resume the treatment, up to completion of the Treatment Phase or the Target Ulcer Closure, whichever is earlier. If Target Ulcer closes prior to 12-week, then the Subject enters the 12-week Follow-Up phase immediately. The 12-week Follow-Up is required to confirm Target Ulcer closure, assess strength of closed Target Ulcer, assess progression of open wounds post Treatment Phase in terms of wound size and AEs, if any.

In this trial, Subjects will be randomized in three Groups viz, Galnobax® plus SoC, only SoC, and Vehicle plus SoC in 3:3:1 ratio. A large population is required to achieve statistically significant efficacy endpoint for wound closure, whereas relatively smaller number of Subjects are sufficient to assess non-deleterious effects of Vehicle gel. During randomization, the Subjects will be stratified based on location as well as size of the Target Ulcer to have a proportional population in the three groups. Since SoC only is the treatment of choice used in clinical setting for DFU presently, this trial uses SoC only as comparator arm to Galnobax® plus SoC treatment for efficacy analysis. The parameters of Vehicle plus SoC arm will be compared with only SoC arm to check if Vehicle has any deleterious effects on wound healing.

The FAS Population (Efficacy Evaluable Population) will include all randomized Subjects who have at least 6 weekly assessments for Target Ulcer Closure or has Target Ulcer closed earlier than 6 weeks. The efficacy analysis in this Study will use FAS Population in order to ensure that Subjects have received reasonable treatment, and are assessed for Target Ulcer Closure by blinded Investigator.

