Endpoints:	
Primary Endpoint:
 
Efficacy endpoint: The efficacy assessment will involve Galnobax® plus Standard of Care and only Standard of Care groups
 
 1. Proportion of Subjects achieving Target Ulcer Closure within 12-week Treatment Phase, as assessed by blinded Investigator. 
Secondary Endpoints:
 
Efficacy endpoints:
 
 1. Time to Target Ulcer Closure during the 12-week Treatment Phase, as assessed by the blinded Investigator. 2. Proportion of Subjects achieving Target Ulcer Closure till End of Study, as assessed by the blinded Investigator. 
Safety endpoints:
 
 1. Proportion of Subjects with treatment emergent adverse events (TEAEs). 2. Proportion of Subjects with events related to the local wound assessment of Target Ulcer in Vehicle plus Standard of Care group.
Study Population:	
A maximum of 350 Subjects will be randomized for this Phase 3 clinical Study who have DFU and satisfy eligibility criteria given below and in Section 5. The break-up of these 350 Subjects is as follows:
 
Group 1: Galnobax® + SoC such that minimum number of Subjects in this group is 120.
 
Group 2: SoC alone such that minimum number of Subjects in this group is 120.
 
Provision for drop-outs in Groups 1 and 2: 20% i.e. 60 Subjects
 
Group 3: Vehicle + SoC such that the maximum number of Subjects in this group is 50 to evaluate the safety of Galnobax® vehicle.
 
Eligibility Criteria
 
a. Inclusion criteria
 
The Subjects who satisfy all the following inclusion criteria will be enrolled in the Study and subsequently randomized:

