9.2 SAMPLE SIZE DETERMINATION

This Study will have FAS Population (Efficacy Evaluable Population) of minimum of 240 Subjects (minimum of 120 each in Group 1 and Group 2). To ensure this and assuming 20% drop out rate, the population of two groups would be up to 300 Subjects. For safety analysis of Vehicle of Galnobax®, maximum of 50 Subjects will be recruited in Vehicle plus SoC group. Thus, overall population of maximum of 350 Subjects will be recruited in the Study.

Sample Size Determination and Rationale:

The sample size calculation has two components. One is based on statistical power and the other is based on clinical judgment.

The sample size calculation is based on the primary endpoint for the Study that is proportion of Subjects achieving complete closure of Target Ulcer within 12-week Treatment Phase, as determined by blinded Investigator's assessment.

The sample size is obtained based on the assumption that there will be a clinically meaningful difference of 21%, (i.e., 39% of SoC vs 60% of Galnobax®-treated achieved complete closure of Target Ulcer, odds ratio of 0.65). This assumption is based on the following:

- a. Literature reports from various DFU trials showed that average percent wounds closed using SoC treatment is 24% globally.^{5 27} However, percent wounds closed using SoC treatment in recently completed DFU trial in India is reported to be 37.8%.²⁸ In view of this, it is assumed that 39% wounds may close in the SoC group.
- b. In Phase 1/2 study of Galnobax®, 60% wounds closed within 12-week of Galnobax® treatment. Furthermore, 67% wounds were closed in Galnobax® arm for wounds with wound age > 6 weeks. In view of this, the inclusion criterion is revised to include Subjects with wounds of at least 6 weeks (which was 4 weeks in Phase 1/2 study) and it is assumed that 60% wounds may close in the Galnobax® treatment group.

To meet the Type I error rate of 0.05 (95% confidence interval), 2-sided analysis and 90% power, 120 Efficacy Evaluable Subjects in Group 1 and Group 2 will be required for making the FAS Population in the Study as 240. To accommodate the potential drop outs rate of 20%, a total of 300 Subjects will be randomized in these Groups to ensure more than 90% power for the primary endpoint analysis (i.e., proportion of Subjects achieving Target Ulcer Closure within 12-week Treatment Phase).

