The safety evaluation of Vehicle of Galnobax® will be done by recruiting population of 50 Subjects in the Vehicle plus SoC group. As there is not hypothesis testing or statistical comparison proposed for this arm, this population might not be statistically significant, but would enough to give reasonable estimate of safety for Vehicle of Galnobax®.

9.2.1 RANDOMIZATION AND STRATIFICATION OF STUDY POPULATION:

Prior to randomization, Subjects will be stratified by location of Target Ulcer (planter or non-planter), and the Target Ulcer size ($<5\text{ cm}^2$ or $\geq 5\text{ cm}^2$). The randomization will be done at the ratio of 3:3:1 in one of the following groups, using an IWRS:

- Galnobax® 14% plus SoC or
- SoC or
- Vehicle plus SoC

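### The Vehicle arm (maximum 50) is called sufficient, and the objective speaks of establishing no harm to healing, but the arm can only describe, and no comparison with SoC is planned in section 9

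*Combined protocol and SAP*

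**What the plan says.** Section 4.2 explains the 3:3:1 allocation by contrasting the large groups needed for efficacy with the Vehicle group, for which a "relatively smaller number of Subjects are sufficient to assess non-deleterious effects of Vehicle gel". It adds that the Vehicle group will be compared with SoC alone to check for harm to wound healing. Section 4.1 also describes Vehicle plus SoC versus SoC as something the study is designed to evaluate.

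The safety objective in section 3, repeated in the synopsis and in section 9.4.4, is worded as "establishing non-deleterious effects of Vehicle on wound healing". The endpoint attached to it is the proportion of subjects with local wound assessment events in the Vehicle group.

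Section 9.2 sets the arm at a maximum of 50. It says that no hypothesis test or statistical comparison is proposed, concedes that the number might not be statistically significant, and holds that it "would enough to give reasonable estimate of safety". Section 9.4.4 covers safety in all three groups without formal analysis. For the vehicle question it tabulates local pain, edema and erythema in the Vehicle group. Sections 9.4.2 and 9.4.3 restrict the closure analyses to Groups 1 and 2.

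**The concern.** Two things do not fit together. First, the stated purpose is to establish an absence of harm to healing, and the size is declared adequate for it, yet no margin, precision or calculation supports that. Second, section 4.2 promises a comparison with SoC that section 9 does not contain: 9.2 proposes none, and 9.4.4 tabulates local signs in one group, with neither the comparator nor closure beside them.

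At stake is what the study report may say about the vehicle. Section 6.1.1 says the Vehicle gel has the same inactive ingredients at the same concentrations as Galnobax, so this arm is the trial's only separate information on the vehicle. As the objective is worded, Vehicle and SoC results that look alike could be described as meeting it, although the data would also fit a sizeable loss of closure.

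**Working it through.** **Inputs**
- SoC closure 39%, Galnobax 60%: section 9.2, "39% of SoC vs 60% of Galnobax®-treated achieved complete closure of Target Ulcer".
- Error rates: section 9.2, "To meet the Type I error rate of 0.05 (95% confidence interval), 2-sided analysis and 90% power".
- Groups 1 and 2: 120 evaluable each; up to 300 randomized, so 150 each (section 9.2).
- Vehicle: maximum 50 (sections 4.1 and 9.2).
- Drop-out: the synopsis has "Provision for drop-outs in Groups 1 and 2: 20% i.e. 60 Subjects". Nothing is provided for the Vehicle arm.
- Assumption 1: Vehicle closure equals SoC closure, 39%. The plan gives no Vehicle rate for this trial.
- Assumption 2, for the lower case only: 20% loss in the Vehicle arm too, leaving 40.

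**The plan's own figure, Groups 1 and 2**

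n per group = [1.96·√(2·0.495·0.505) + 1.2816·√(0.39·0.61 + 0.60·0.40)]² / 0.21² = (1.386 + 0.886)² / 0.0441 ≈ 117.0, rounded up to 118. The planned 120 gives 90.7% power, and 240/0.8 = 300. The main sample size reproduces. No corresponding figure is stated for the Vehicle arm, so there is none to reproduce.

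**Precision of Vehicle minus SoC for closure**

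SE = √[0.39·0.61·(1/nV + 1/nS)]; half-width = 1.96·SE.

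| Vehicle | SoC | SE | 95% half-width |
|---|---|---|---|
| 50 | 150 | 0.0796 | 15.6 points |
| 50 | 120 | 0.0821 | 16.1 points |
| 40 | 150 | 0.0868 | 17.0 points |
| 40 | 120 | 0.0891 | 17.5 points |

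Against the 21-point design effect, 15.6/21 = 74% and 17.5/21 = 83%.

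**Sensitivity to the rate and the method**
- 24% in both arms (the global SoC figure in 9.2): 13.7 to 15.3 points.
- 37.8% (the Indian trial cited in 9.2): 15.5 to 17.4 points.
- 43% (placebo, older ulcers, Phase 1/2, section 2.2): 15.8 to 17.7 points.
- Newcombe limit on the loss side at 39%: 14.6 to 16.2 points.
- One-sided 95% bound at 39%: 13.1 to 14.7 points.

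**What the arm could show** (range over 50 vs 150 and 40 vs 120)
- If the vehicle is harmless, P(the interval excludes a loss of m) = Φ(m/SE − 1.96). For m = 10 points: Φ(0.10/0.0796 − 1.96) = 24%, and Φ(0.10/0.0891 − 1.96) = 20%. For m = 17 points: 57% and 48%.
- A true fall from 39% to 24% would reach two-sided p < 0.05 in 48% and 40% of trials.
- The loss detectable with 80% power is 20.8 to 23.0 points, about the whole design effect.

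**The declared endpoint, local events**

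Zero events in 50 leaves a one-sided 95% upper bound of 1 − 0.05^(1/50) = 5.8%. The two-sided 95% equivalent is 1 − 0.025^(1/50) = 7.1%. That is informative about local reactions. It does not measure closure.

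**The case against.** The best defence is that the plan already says this where it sizes the arm. Section 9.2 disclaims any test and concedes limited statistical weight, and 9.4.4 rules out formal analysis. To assess is not to exclude, and section 4.1 speaks of investigating harmful effects, if any. The endpoint declared for the objective is local events, not closure. No passage gives a rule that similar results will be reported as no harm.

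Much of this stands. This is not a failed power calculation or an arithmetical error, because no power, margin or precision is claimed for the arm. How the results would be reported is an inference from the objective's wording. What the defence does not do is repair section 4.2 or the objective. The disclaimer in 9.2 conflicts with the comparison promised in 4.2, and the wording about establishing no harm to healing remains in three places. Local signs alone cannot answer a question about healing.

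Three stronger readings are tempting and are not supported:
- *The arm can never exclude a loss of 16 to 17 points.* The interval is centred on the observed difference. The statement fits an observed difference of zero; with a harmless vehicle, a 17-point loss would still be excluded in roughly half of trials.
- *The primary result is compromised.* Galnobax contains the vehicle, so Galnobax plus SoC versus SoC is already net of any vehicle effect.
- *The arm must be enlarged.* A descriptive aim does not require it.

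**Conclusion.** The concern holds as a mismatch between the stated conclusion and what the arm and its planned analysis can deliver. With about 50 Vehicle subjects, an observed zero difference in closure would leave losses of up to about 15.6 points (50 vs 150) or 17.5 points (40 vs 120) inside the two-sided 95% interval. The arm can describe the vehicle's effect; it cannot establish absence of harm to healing. Sections 4.2, 9.2 and 9.4.4 also disagree on whether a comparison with SoC is made at all.

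Of the rates used, only the 39% for SoC is the plan's. The equal Vehicle rate and the 40 evaluable Vehicle subjects are assumptions. Other rates found in the documents move the half-width only within 13.7 to 17.7 points, which does not change the conclusion. The matter is worth correcting because it limits what may be concluded about the vehicle; it leaves the sample size and the primary analysis as they are.

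**What to change.** 1. Section 4.2: replace *are sufficient to assess* with *give a descriptive estimate only of*.
2. Synopsis, section 3 and section 9.4.4: replace *establishing* with *estimating* in the Vehicle objective.
3. Section 9.4.4: tabulate local wound events and Target Ulcer Closure for Vehicle plus SoC and SoC alone side by side, with the difference and its 95% confidence interval and no hypothesis test. Name the analysis population, and state the expected precision for closure, about ±16 to ±17 points.
4. Section 9.2: keep the statement that nothing is tested, and refer to this descriptive comparison, so that 4.2, 9.2 and 9.4.4 agree.
5. Add: *A similar or non-significant result for Vehicle and SoC will not be reported as evidence that the vehicle does not impair healing.*

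The cost is one extra descriptive table and a less favourable stated claim for the Vehicle arm. No subjects are added, and the primary and secondary efficacy analyses stay limited to Groups 1 and 2.
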